**(5) Data Collection Methods, Assessments, Interventions and Schedule (what assessments performed, how often)**

*Consent process:* Research staff from the Division of Sports Medicine will complete the consenting process with the participants and their parents/guardians (if necessary) prior to any testing. The research staff member will explain the project and review the consent/assent form. The subject will review the consent form with their parent/legal guardian. The subjects and their parents will be given adequate time to review the study materials and ask questions. If they choose to participate, the patient and parent will sign the IRB approved consent/assent forms. It will be made clear to the patient and their parents that participation in the study is voluntary. They will be informed during the explanation of the study that their decision to participate or not will not affect their medical treatment at Boston Children's Hospital.

***Data collection methods:***

Height/Weight

Cerebral blood flow: NIRS and TCD systems

CO2 levels obtained during the study session and exercise

Blood Pressure obtained during the study session and exercise

Heart Rate: 5 lead ECG during the study session and exercise

Rate of Perceived Exhaustion: Borg Scale

Post-concussion symptom inventory: PCSI, PCSS, CSI

Single/ dual-task gait assessments at rest before exercise

Aerobic Activity: Polar Wrist Units with Heart Rate Monitors

Anxiety, Dizziness and patient health surveys are measured by the following scales: Dizziness

Handicap Scale (DHS), Hospital Anxiety and Depression Scale (HADS), Patient Health Questionnaire (PHQ)

The protocol consists of measurements and procedures that have no known risks and have been routinely used in laboratory studies as well as other human physiology and biomechanics labs without any adverse events. Throughout each examination, the electrocardiogram will be monitored using a standard 5-lead ECG via wires attached to the chest via hypoallergenic adhesive electrodes. Blood pressure will be monitored every 2 – 4 minutes via a standard oscillometric blood pressure cuff attached to the upper arm, and monitored continuously via a photoplethysmographic finger cuff on the index or middle finger.

The attachment and removal of ECG electrodes and inflation of the blood pressure cuff may cause mild discomfort (though no more than routine physical examinations), but there are no risks associated with any of these measurements.

Cerebral blood flow will be measured via ultrasound with a Doppler probe placed on the left and right temple and a NIRS probe placed on the forehead contralateral to the dominant hand. There are no known risks associated with transcranial ultrasound or near infrared spectroscopy. We routinely use both (currently, in over 50 young individuals) with no reported discomfort or ill effects.

***Schedule:***

Recruitment: Potential concussed subjects will be recruited from the sports medicine clinic at Boston Children's Hospital by a research staff member. If the subject is eligible and interested in participating they will schedule study visit 1 with the research staff member.

Study Visit 1 (time of enrollment):

Subjects will come to The Micheli Center for Sports Injury Prevention or Spaulding Hospital in Cambridge for a two hour visit. Once they give consent we can schedule a time for testing.

Subjects will be measured for height and weight. Subjects will complete a short medical history questionnaire, which includes the DHS, HADS, PHQ and a PCSI/ PSCC. Subjects will then be fitted for a Polar Wrist Unit and Heart Rate Monitor. During this time, they will also have a standard 5-lead ECG placed by a trained research member. Additionally, a research member will attach a blood pressure cuff to their non-dominant arm and to their middle finger (for photoplethysmographic measurements) and set up to the TCD and NIRS system. Both the usual care group and intervention group will complete this part of the study.

The first part of the study procedure involves supine rest, performing mental tasks, CO2 rebreathing, and resistance breathing to induce small periodic oscillations in arterial pressure. For resistance breathing, volunteers will breathe through a mouthpiece attached to a standard impedance threshold device made from latex-free PVC (PowerBreathe) set-up to moderate breathing resistance (10-20 cmH2O). There are no risks associated with mental or physical tasks (N-Back and finger tapping tasks) or resistance breathing. The CO2 re-breathing may cause slight lightheadedness in some people; however, this can be reversed almost immediately by switching them back to room air. Both usual care and intervention groups will complete this part of the study.

The second part of the procedure involves the branching graded exercise test. Subjects will still be monitored using a standard 5-lead ECG and blood pressure measured by oscillometric blood pressure cuff. Throughout the graded exercise test cerebral blood flow will be monitored via TCD or NIRS. The subjects will also be connected to the metabolic cart to measure VO2. The exercise test will continue until the subject reports an increase in symptoms, using the abbreviated concussion symptom inventory or to 85% of their age-predicted maximum heart rate determined by the 5-lead ECG. The subject will be taken off the bike and cool down. Measurements will be taken for an additional five minutes. Both the usual care and intervention group will complete this part of the study.

After completion of testing, the subject will have the ECG, blood pressure cuff, metabolic cart, TCD and NIRS system removed. They will be monitored by a trained professional until symptoms ease or subject's heart rate and blood pressure has returned to resting values.

The final part of the procedure includes the single/ dual-task gait evaluation and VOMS.

Weeks 1-4 (at-home exercise):

Subjects in the intervention group will be advised to participate in aerobic exercise five days a week. This includes walking, biking, jogging and running. While participating in these activities, they will be wearing their Polar Wrist Unit and Heart Rate Monitor to help subjects track their exercise intensity. They will exercise for 20 minutes five times a week at 80% of their heart rate reverse, determined by their resting heart rate and maximum heart rate reached during exercise testing.

Usual care subjects will follow their physician's instructions for exercise and rest. They will also wear the Polar Wrist Unit and Heart Rate Monitor to track their exercise intensity, but will not receive a heart rate specific exercise recommendation.

Study Visit 2 (approximately 4 weeks post-enrollment):

All participants will participate in this visit. Subjects will undergo the same procedures as visit one, including the DHS, HADS, PHQ, PCSI/ PCSS, supine rest, graded exercise test, VOMS and

single/dual- task gait. At this time, the target heart rate for exercise will be adjusted to a new symptom limited heart rate for all participants who are still symptomatic based on the same procedure.

#### Weeks 4-8:

Subjects will continue to participate in aerobic activity as specified above, monitored by their Polar Wrist Unit and Heart Rate Monitor. Usual care subjects will continue to follow their physician's recommendations.

#### Study Visit 3 (8 weeks post-enrollment):

All subjects will participate in this visit (usual care and intervention). Subjects will undergo the same procedures as visit one, including completing the DHS, HADS, PHQ, PCSI/PCSS, cerebrovascular function tests, graded exercise test, VOMS and single/ dual-task gait.

### **(6) Study Timeline (as applicable)**

Once IRB approval is given we will start the recruitment process. We plan to enroll and complete testing for a total of 60 subjects over the next year.

Timeline for all subjects:

- Recruited from Boston Children's Hospital Sports Medicine clinic
- Comes in within 14 days of injury for study 1 visit
- Comes in 4 weeks later for study 2 visit
- Comes in 4 weeks later for study 3 visit

### **E. Adverse Event Criteria and Reporting Procedures**

There are no known risks associated with near-infrared spectroscopy or transcranial Doppler ultrasound and the anticipated volunteer discomfort due to instrumentation and measurements is not more than that of a routine physical exam. The probability and magnitude of harm or discomfort anticipated during the experimental protocols are not greater than those ordinarily encountered in routine daily life. There is the possibility that exercise triggers concussion symptoms however exercise will be stopped immediately upon reporting of increased symptoms and patients will be monitored until resolution of symptoms. Risk of exercise in concussion may occur in the setting of acute injury (within the first 72 hours), however, there is no known harmful effect of exercise in sub-acute or chronic mild TBI. In fact, recent research suggests that sub-symptom threshold exercise may aid in recovery. If any adverse event occurs, they will be reported immediately to the CCI.

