## **(2) Patient Selection and Inclusion/Exclusion Criteria**

### **Inclusion**

- Male or females between 14-21 years of age
- Experienced a concussion within 14 days of testing, defined as a person who has had a traumatically induced physiological disruption of brain function, manifested by at least one of the following:
  - Any period of loss of consciousness;
  - Any loss of memory for events immediately before or after the accident;
  - Any alteration in mental state at the time of the accident (ie., feeling dazed, disoriented, or confused)
  - Symptoms of nausea, dizziness, fatigue, headache, or changes in sleep, cognition or, emotions following the accident
- Low or moderate cardiac risk according to American College of Sports Medicine (11)

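### Section E names the first 72 hours after concussion as a possible exercise risk, but no minimum time since injury is set, so Visit 1 exercise testing and home exercise may start inside that window

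*Combined protocol and SAP*

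**What the plan says.** On risk, Section E states: "Risk of exercise in concussion may occur in the setting of acute injury (within the first 72 hours". The reassurance that follows is limited to later stages: "there is no known harmful effect of exercise in sub-acute or chronic mild TBI".

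On timing, the inclusion criterion in Section D(2) reads "Experienced a concussion within 14 days of testing", and the timeline in Section D(6) reads "Comes in within 14 days of injury for study 1 visit". No exclusion criterion concerns time since injury. Section D(5) heads the first visit "Study Visit 1 (time of enrollment" and says of eligible, interested patients that "they will schedule study visit 1 with the research staff member". It gives no minimum interval.

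On exposure, Section D(5) puts a graded cycle test in Visit 1 for both arms: "The exercise test will continue until the subject reports an increase in symptoms", or until 85% of age-predicted maximum heart rate. The intervention arm then exercises at home for 20 minutes, five times a week, during weeks 1 to 4. The target is 80% of heart rate reserve (printed as reverse), calculated from resting heart rate and the maximum reached in the test. No start day is given.

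**The concern.** The safety argument and the entry rule do not cover the same period. Section E divides time after injury into an acute part, where exercise may carry risk, and a later part, where none is known. The entry rule ignores that division. A patient injured the day before could be enrolled, tested to 85% of age-predicted maximum heart rate and, if assigned to the intervention, started on home exercise, with every written rule respected.

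What is at stake is participant safety and clarity for those who approve and run the study. Participants are 14 to 21 years old, so some are minors. A reader cannot tell whether testing in the first three days is intended or an oversight.

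**Working it through.** The protocol gives no figure to reproduce here. The check compares every rule on time since injury with the 72-hour statement.

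**Step 1. Rules on time since injury**

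| Place | Lower limit | Upper limit |
|---|---|---|
| D(2) Inclusion | none | 14 days |
| D(2) Exclusion | none | none |
| D(5) Schedule, Visit 1 | none | none |
| D(5) Schedule, home exercise | none (no start day) | none |
| D(6) Timeline | none | 14 days |
| E, risk statement | 72 hours implied, not made a rule | none |

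**Step 2. Overlap**

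- Permitted window for Visit 1: 14 × 24 = 336 hours.
- Flagged period: 72 hours, or 3 days, lying wholly inside that window.
- Share of the window: 72 / 336 = 21%. This is a share of permitted time. It does not estimate the share of participants.

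**Step 3. Most who could be exposed**

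- Section D(1) plans up to 60 participants, equally randomized: 60 / 2 = 30 per arm.
- The ceiling is therefore 60 taking the graded test and 30 assigned home exercise. The documents give no distribution of time from injury to Visit 1, so the actual number cannot be derived.
- Home sessions per person, assuming one session every 24 hours from the day after Visit 1: a visit at hour *t* gives sessions at *t* + 24, *t* + 48 and so on. With *t* under 24, two fall before hour 72; from 24 to under 48, one; from 48 on, none. The range is 0 to 2.

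**Step 4. Does any safeguard act on time since injury?**

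- Low or moderate cardiac risk at entry (D(2)): no.
- Stopping on increased symptoms (D(5), E) or any discomfort (G): no. It acts once exercise has provoked something.
- Constant observation in a supervised facility (G): no, and it covers visits only.
- Post-test monitoring (D(5): "They will be monitored by a trained professional until symptoms ease", or until heart rate and blood pressure return to resting values): no.
- Home intensity: target = resting rate + 0.80 × (maximum reached − resting rate). A participant who stops early with symptoms has a lower maximum and so a lower target. This limit does reach home sessions, but it follows symptoms on test day and not time since injury.

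**Step 5. Is there a rationale for including the first 72 hours?** Section B supports early exercise over the first 10 days as a whole. That range includes days 0 to 3 but says nothing particular about them. In the text available, only Section E singles them out, and it does so as a possible risk.

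**Step 6. Window after a lower limit:** 14 − 3 = 11 days, or 11 / 14 = 79% of the present length.

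**The case against.** The best defence is that the plan manages risk by symptoms instead of by calendar. The one harm Section E describes concretely is the triggering of concussion symptoms, and its answer is to stop at once and monitor. The test is symptom-limited, and so is the home dose derived from it. Section E also rates the expected harm as no greater than that of daily life, and its 72-hour sentence says only that risk may occur. Recruitment through a clinic, followed by a booked visit, makes very early testing less likely. Section B supplies a general case for early exercise.

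Most of this stands, and it limits the weight of the point. It does not remove the gap. The 72-hour sentence names no mechanism, so it cannot be shown that stopping on symptoms covers whatever risk is meant. Section E separates acute from later injury even though the stopping rule applies to everyone. Booking makes delay plausible without requiring it, and Section D(1) also lists schools and sports organizations as sources of participants.

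A reader might go further and infer that many participants will be exercised in the acute phase, that home sessions are unprotected, or that the plan gives no reason for early exercise. The documents support none of these. They give no data on time to Visit 1, they limit home intensity individually, and Section B does offer a rationale, though one not specific to the first 72 hours.

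**Conclusion.** The inconsistency holds on the text: exercise is permitted in a period that Section E flags as possibly risky, and no rule excludes that period or justifies it specifically. The change is recommended because it is cheap and concerns safety. The point does not affect the sample size, the power or the validity of the analysis.

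The ceiling is 60 tested and 30 assigned home exercise. The actual number is unknown and may be small. Under the stated assumption on session timing, early home exposure would be at most two 20-minute sessions per person.

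Confidence is high for the textual gap and much lower for its practical consequence. The conclusion rests on the text available for review, in which some pages, including whatever stands between Sections I and K, are absent. A minimum interval stated there would settle the matter.

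**What to change.** Amend the inclusion criterion in D(2) and the timeline in D(6) so that Visit 1 takes place more than 72 hours and no more than 14 days after injury. Home exercise follows Visit 1, so the same limit covers it. A patient who presents sooner is booked at the first slot after 72 hours, using the scheduling step already in D(5).

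The cost is a short amendment in two places. No new data item is needed, because the 14-day rule already requires the injury date. The window falls from 14 to 11 days, which may slow recruitment slightly. Days 0 to 3 are lost from Aim 1 and from the Section H comparison across injury duration.

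If the sponsor wants those days, a specific justification in Section E for exercising within 72 hours would also resolve the inconsistency. Deferring only the graded test and home exercise would keep the early resting measurements, but it splits Visit 1 in two; moving the whole visit is simpler.

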### **F. Data Management Methods**

Medical health information will be saved and input using RedCap survey. There will be an internal RedCap to enter recruitment information and identifying information. It will also include the exercise logs to help blind the PI from knowing which intervention group the subjects are in. The external RedCap will include the surveys, concussion history and test measurements. The information will be stored using the study ID numbers consistent with the rest of the measurements. Data from the heart rate monitors will be securely transferred from the device to a BCH-encrypted computer via USB drive.

### **G. Quality Control Method**

As these studies represent physiologic investigation and not clinical trials, no formal quality assurance programs will be implemented. However, the ongoing results, problems, and limitations of the study will be overseen by the P.I. Studies will be conducted in a well-supervised hospital facility and

subjects will be under constant observation by skilled professionals. Appropriately certified and registered laboratory personnel will be present during the procedure. Procedures will be stopped if the volunteer exhibits any discomfort.

Any adverse events will be promptly reported to the Human Research Committee for review according to HRC guidelines. Serious adverse events either expected or unexpected will be reported immediately (within 24 hours of event) by telephone, fax or email followed by a full written report using the PHRC Adverse Event Form within 10 working days/14 calendar days. Mild to moderate unexpected or expected adverse events will be reported in writing using the PHRC Adverse Event Form within 20 working days/30 calendar days.

Information about particular subjects will be known only by study team. To maintain confidentiality, subject data will be referenced by number and identifying information will not be used during discussion, presentation, or publication. Spaulding Hospital certifies key personnel have completed education on the use of human subjects in compliance with NIH regulations.

## **H. Data Analysis Plan**

This protocol seeks to elucidate the relationship between regional brain blood flow and CO2 during exercise in individuals who have experienced a mild TBI, and to assess the effect of a standardized exercise protocol on cerebral blood flow.

Total hemoglobin concentration in the pre-frontal cortex will be calculated as the sum of oxygenated and deoxygenated hemoglobin (as measured by NIRS) and will serve as a surrogate for regional cerebral blood flow. The brain blood flow and end-tidal CO2 data will be aligned in time. The linear relationship between the two time series will be determined and compared across injury duration and symptom severity. We will use a linear mixed effect model akin to a multiple linear regression model where regional cerebral blood flow is used as the dependent variable, end-tidal CO2 is the independent variable, and symptom duration and amount of exercise are covariates.

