- *Static postural stability:* As the Balance Error Scoring System (BESS) test is typically performed as a part of the clinical exam, participant performance will also be documented. During the BESS, three experimental trials are performed with eyes closed in 3 conditions: double-leg stance, single-leg stance, and tandem stance. During double-leg stance, participants are instructed to stand with their feet positioned side by side. For the single-leg stance condition, participants stand on the foot that they identified as their non-dominant kicking leg. The tandem stance condition consists of participants standing with their feet positioned where the non-dominant foot is placed directly behind the dominant foot. Each trial is performed for 20 seconds. When available, participants will perform the test on an instrumented motion capture-force platform system.

Estimated time to complete the single and dual-task balance assessment is approximately 8 minutes. The order of assessments will be rotated for each visit, but consistent for all subjects.

Heart rate will be monitored via a standard 5-lead ECG.

Cerebral blood flow will be monitored via Near-Infrared Spectroscopy (NIRS) and transcranial Doppler ultrasound (TCD). NIRS will be measured with a probe placed on the forehead contralateral to the dominant hand. NIRS-derived blood oxygenation levels will be used as a measure of cerebral blood flow at the prefrontal cortex. TCD will be measured with probes placed bilaterally on both sides of the head slightly behind the temples. TCD derived blood flow velocities on middle cerebral arteries will be used as a measure of global cerebral blood flow. The TCD protocol used will be exactly the same as the active and IRB-approved protocol (Protocol number: 8926) within this study.

Arterial blood pressure will be monitored continuously via a photoplethysmographic finger cuff on the index or middle finger throughout the study session and via a standard oscillometric blood pressure cuff attached to the upper arm. Pressure measurements will be obtained only via oscillometric blood pressure cuff during the graded exercise.

[figure not shown]
End-tidal CO2 will be monitored using infrared analyzer (Model 17515A, VacuMed) connected to a nasal cannula.

Rate of Perceived Exhaustion (RPE) will be monitored by a visual Borg rating of perceived exertion during the graded exercise test

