**Figure 1: Modified sub-maximal exercise protocol**

#### **(4) Definition of Primary and Secondary Outcomes/Endpoints**

- Primary: blood oxygenation level in the prefrontal cortex before and after the administration of the exercise protocol.
- Secondary: the proportion of participants who continue to experience symptoms after the 8-week exercise intervention and the potential confounding variables that contributes to this risk of persistent symptoms.

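### The primary endpoint is prefrontal blood oxygenation, but the only planned analysis models total haemoglobin, a different quantity, so the declared endpoint has no analysis

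*Combined protocol and SAP*

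**What the plan says.** Three sections of the combined protocol and SAP describe the prefrontal NIRS measurement.

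- D(4), the endpoint definition: "Primary: blood oxygenation level in the prefrontal cortex before and after the administration of the exercise protocol".
- D(3), the measurement methods: "NIRS-derived blood oxygenation levels will be used as a measure of cerebral blood flow at the prefrontal cortex".
- H, the analysis plan: "Total hemoglobin concentration in the pre-frontal cortex will be calculated as the sum of oxygenated and deoxygenated hemoglobin". H says that this sum "will serve as a surrogate for regional cerebral blood flow", and specifies one linear mixed effect model in which "regional cerebral blood flow is used as the dependent variable". End-tidal CO2 is the independent variable; symptom duration and amount of exercise are the covariates.

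No section says whether blood oxygenation level means oxygenated haemoglobin, the difference between the two forms, or saturation. Section I sizes the study on the relation between regional blood flow and CO2, as H does, and does not mention oxygenation.

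On recording, the Visit 1 text in D(5) says: "Throughout the graded exercise test cerebral blood flow will be monitored via TCD or NIRS". D(3) and the data collection list in D(5) give NIRS and TCD together.

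**The concern.** The variable named as primary and the variable analysed are not the same. Total haemoglobin measures how much haemoglobin is in the sampled tissue; oxygenation depends on how that amount divides between its two forms. Followed as written, the plan reports a model of the total and never analyses the declared endpoint.

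Both quantities come from one NIRS recording. An analyst could report total haemoglobin and cite H, or report oxygenation and cite D(4), and could make that choice after seeing both. D(1) describes the study as non-blinded. Section F keeps the exercise logs in a separate database to help blind the PI to group, but that does not fix the choice of variable. What is at stake is whether the primary result was fixed in advance.

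**Working it through.** The plan gives no figure on this point. The R² of 0.31 in Section I concerns the flow–CO2 relation and does not bear on which NIRS variable is primary.

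**Step 1: definitions.** Let O be oxygenated and D deoxygenated haemoglobin. Section H's variable is T = O + D. As D(4) does not define oxygenation, take its three plausible readings: O itself, the difference O − D, and saturation S = O/T.

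**Step 2: total constant, oxygenation changes.** Let O rise by x and D fall by x. Then T is unchanged, O rises by x, O − D rises by 2x, and S rises by x/T. All three readings move and Section H's variable does not.

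**Step 3: oxygenation constant, total changes.** This is also possible on each reading:

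- multiplying O and D by the same factor leaves S unchanged and multiplies T by that factor;
- adding the same amount to both leaves O − D unchanged and raises T by twice that amount;
- changing D alone leaves O unchanged and moves T.

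**Step 4: numbers.** These values are assumed, in arbitrary units; the documents give none.

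| O / D | T = O + D | O − D | S = O/T |
|---|---|---|---|
| 60 / 40 | 100 | 20 | 60% |
| 66 / 34 | 100 | 32 | 66% |
| 72 / 48 | 120 | 24 | 60% |

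From the first row to the second, x = 6: saturation rises by 6/100, or 6 percentage points, the difference rises by 12, and the total does not move. From the first row to the third, both parts are multiplied by 1.2: the total rises by 20% and saturation does not move. A second assumed set gives the same picture: 45/25, 50/20 and 40/30 all total 70, with saturations of 45/70 = 64.3%, 50/70 = 71.4% and 40/70 = 57.1%.

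**Step 5: does H analyse the D(4) contrast at all?** D(4) asks for a comparison before and after exercise. The terms listed in H are end-tidal CO2, symptom duration and amount of exercise. None is a before/after, visit or arm term. D(4) also leaves open whether the exercise protocol is the single graded test or the 8-week programme. Giving D(4) and H the same variable name would therefore not, by itself, supply an analysis of the endpoint.

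**Step 6: the recording text.** D(3) and the data collection list in D(5) specify both systems. The Visit 1 text sets subjects up on both before testing and removes both only after testing is complete. The one *or* stands against all of these. D(3) assigns TCD to middle cerebral artery velocity, as a measure of global flow, so TCD could not replace NIRS for either prefrontal variable.

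**The case against.** The best defence is that D(3) and H aim at the same thing. D(3) calls NIRS oxygenation a measure of prefrontal blood flow, H calls total haemoglobin a surrogate for regional blood flow, and both come from the same signal. Only H gives a formula, and Section I is consistent with it. On this view H simply makes a loosely named endpoint operational.

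Part of this stands. H is probably what was intended, and since no oxygenation analysis is specified, the room for a later choice is limited to D(4) being cited in support of one. But H never says that it is analysing the D(4) endpoint, and the sum is not oxygenation on any of the three readings. Two unranked proxies for one construct still leave the primary variable unsettled.

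It also stands that the worked values were chosen to make the quantities separate cleanly. They show that the two can diverge, not that they would do so materially in these patients.

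A reader might infer from the *or* in D(5) that some exercise tests will lack NIRS data. The documents do not support this: both systems are fitted before testing and removed after it, and no section describes a session recorded by TCD alone. The word is most plausibly loose drafting.

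**Conclusion.** The point holds as a contradiction between the endpoint definition and the analysis plan. D(4), with D(3), declares one NIRS quantity primary, H analyses another, and the declared one has no planned analysis. This follows from the definitions and needs no assumption about physiology or about which reading of oxygenation is meant.

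Its effect on the result cannot be sized from the documents. The 6-point and 20% shifts are illustrations under assumed values. A reader might go further and infer that the two variables will give conflicting answers; nothing in the documents shows that.

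The matter should be settled before outcome data are examined, because the ambiguity concerns the primary variable. The TCD/NIRS wording is minor and adds no weight to this conclusion.

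**What to change.** Name one primary NIRS variable and use it in D(3), D(4) and H. Either route resolves the mismatch:

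1. Restate D(4) as prefrontal total haemoglobin by NIRS, and define an oxygenation measure, with its formula, as secondary. This needs the fewest changes, since it matches the formula in H and the regional-flow target of H and I.
2. Keep oxygenation as primary, define it by formula in D(3) and D(4), and make it the dependent variable in H.

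Under either route, H must say how the chosen variable is analysed for the before/after endpoint: which two time points are compared, whether these are around the graded test or the 8-week programme, and which model term carries the contrast.

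As a minor correction, change TCD *or* NIRS to TCD *and* NIRS in the Visit 1 text of D(5), to agree with the rest of the protocol.

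No new equipment, visits or participants are needed, since both quantities come from one recording. The cost is that this amends a primary endpoint: the change must be dated and justified, with a statement of whether any outcome data had been examined by then.
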